11.2. Analysis of Outcome Measures/Endpoints

Evaluable patients are those that have had all baseline study measures recorded, including having had a fluciclovine (¹⁸F) PET/CT scan.

Evaluation of fluciclovine (¹⁸F) PET/CT

Evaluation of the fluciclovine (¹⁸F) PET/CT images will be primarily reviewed by site-based investigator(s) (as per standard of care). Image interpretation will be based on guidelines derived from an international fluciclovine (¹⁸F) reader consensus meeting held in June 2014. All readers will undergo training in interpretation of fluciclovine (¹⁸F) scans, and will have a training set available for reference. The investigators will have access to all the conventional imaging and medical record information.

The summary of findings will be documented on the appropriate CRF, in addition to a conventional imaging report issued as per standard of care in the respective institution.

Primary endpoint

The primary endpoint of clinical impact of fluciclovine (¹⁸F) in affecting treatment decisions will be assessed by record of the revised treatment plan post fluciclovine (¹⁸F) PET/CT scan in comparison to the pre-scan intended treatment plan.

Secondary endpoints

Improvement in outcome of radical salvage treatment based on fluciclovine (¹⁸F) PET/CT being included in the assessment.

This will be assessed as the proportion of these patients who have a treatment response or treatment failure, using the following definitions:

1. Treatment response
 - a. ≥50% decline in PSA [5] ±
 - b. Radiological response
2. Treatment failure
 - a. Increase or <50% decline in PSA ±
 - b. Radiological progression

PSA threshold

The positive detection rate will be calculated for the overall cohort and across a range of PSA values, to determine the optimum PSA threshold for lesion detection.

Safety assessment

Safety will be assessed from data on the occurrence of adverse events (AEs) and changes in clinical laboratory tests, vital signs, injection-site status, and physical examination findings from the time of administration of fluciclovine (¹⁸F) injection throughout the study period. This has been described in detail in Section 9.

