3.5 Rationale for accurate imaging in BCR

As mentioned previously, the presence of disease outside the prostate bed precludes radical salvage therapy based on mainstream practice. In addition, more favorable outcomes from salvage therapy are observed at low PSA levels [38], when the diagnostic performance of current imaging options is poor. Conversely, the presence of a high PSA is associated with an increased risk of metastatic disease [44], the presence of which precludes the option of radical salvage therapy. Herein lies the ongoing need for an imaging test to detect sites of recurrent disease earlier and with greater accuracy, to aid clinical management in patients with BCR.

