4. OBJECTIVES AND OUTCOME MEASURES/ENDPOINTS

Objectives	Outcome Measures/Endpoints

Primary Objective
 
To confirm the clinical benefit of fluciclovine (¹⁸F) PET/CT in affecting management decisions in patients with BCR being considered for radical salvage treatment (with curative intent).
	
The record of the revised management plan post fluciclovine (¹⁸F) PET/CT scan in comparison to the pre-scan intended management plan.

Secondary Objectives
 
 1. To assess possible improvement in outcome of radical salvage treatment based on fluciclovine (¹⁸F) PET/CT being included in the assessment. 2. To assess the prostate specific antigen (PSA) threshold for positive lesion detection by fluciclovine (¹⁸F) PET/CT in BCR 3. To assess the safety of fluciclovine (¹⁸F) injection in patients undergoing PET/CT 4. 	
 1. The proportion of patients who have a sustained response to radical salvage therapy. 2. PSA levels in relation to scan positivity will be analysed to determine the optimal PSA threshold for detecting recurrent PCa by fluciclovine (¹⁸F) PET/CT. 3. Safety will be assessed from data on the occurrence of adverse events (AEs) and changes in clinical laboratory tests, vital signs, injection-site status, and physical examination findings from the time of administration of fluciclovine (¹⁸F) injection throughout the study period. 4. .

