6.2. Inclusion Criteria

- (1) The subject is a male ≥ 18 years old.
- (2) The subject has had an original diagnosis of PCa and underwent radical curative therapy at least 3 months before enrolment, and has been diagnosed with BCR on the basis of:
 - a. Post RRT / brachytherapy: Increase in PSA level ≥ 2.0 ng/mL above the nadir level after radiotherapy (RT) or brachytherapy (ASTRO-Phoenix criteria) [53], or
 - b. Post RP: EITHER two consecutive rises in PSA and final PSA > 0.1 ng/mL OR three consecutive rises in PSA. This definition is also applicable to subjects with PSA persistence post RP (where the PSA fails to fall to undetectable levels).
 - i. In addition, the subject post RP, should have a PSA doubling time of ≤ 15 months OR PSA level ≥ 1.0 ng/mL at time of recruitment. The PSA doubling time will be calculated using the Memorial Sloan Kettering Cancer Center nomogram (<http://www.mskcc.org/nomograms/prostate/psa-doubling-time>), based on a minimum of two PSA levels within 12 months of screening, taken after the last recorded nadir PSA available at time of screening.
- (3) The subject has not had previous recurrences of PCa, i.e. this is the first diagnosis of BCR.
- (4) The subject is being considered for radical salvage therapy.
- (5) The subject is able and willing to comply with study procedures, and signed, dated and timed informed consent is obtained before any study-related procedure is performed.
- (6) The subject's Eastern Cooperative Oncology Group [ECOG] performance status 0-2.
- (7) The subject should not have received androgen-deprivation therapy within 3 months of screening.
- (8) The subject has a normal or clinically acceptable medical history and vital signs findings at screening (up to 14 days before administration of study drug).

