7.4. Randomisation, blinding and code-breaking

All participants will receive fluciclovine (¹⁸F) injection.

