5 EFFICACY EVALUATION

All listings will be based on the FAS unless specified otherwise. The primary efficacy analysis will be based on the EAS and will be repeated on the PPS as a secondary analysis. The secondary efficacy analyses will be based on the FAS.

Date: 10OCT2018 Version: Amendment 1 Final

5.1 **Primary Efficacy Variable**

The primary efficacy variable is the record of the revised management plan post fluciclovine (¹⁸F) PET/CT scan in comparison to the pre-scan intended management plan.

5.2 **Secondary Efficacy Variables**

The secondary efficacy variables are:

- The proportion of subjects who have a sustained response to radical salvage therapy.
- PSA levels in relation to scan positivity will be analysed to determine the optimal PSA threshold for detecting recurrent PCa by fluciclovine (18F) PET/CT.

Definition of Region Levels

Two main regions will be analysed, the prostate and prostate bed and the extraprostatic region.

The prostate and prostate bed include the following lesion locations:

- Prostate bed left
- Prostate bed right
- Peripheral zone left
- Peripheral zone right
- Central gland left
- Central gland right
- Left seminal vesicle
- Right seminal vesicle

The extra-prostatic regions include the following lesion locations

- Lymph nodes
 - Pelvic lymph nodes
 - Common iliac left
 - Common iliac right
 - Internal iliac left
 - Internal iliac right
 - External iliac left
 - External iliac right
 - Obturator left
 - Obturator right
 - Pre-sacral left

- Pre-sacral right
- Peri-rectal anterior
- Peri-rectal posterior
- Peri-rectal left
- Peri-rectal right
- Inguinal left
- Inguinal right

- Retroperitoneal lymph nodes
 - Para-aortic
 - Retro-aortic
 - Para-caval
 - Retro-caval
- Other lymph nodes
 - Intra-peritoneal
 - Mediastinal left
 - Mediastinal right
 - Axillary left
- Soft tissues/parenchyma
 - o Lung upper lobe left
 - Lung upper lobe right
 - Lung middle lobe right
 - Lung lower lobe left
 - o Lung lower lobe right
 - Brain left
 - o Brain right
 - Liver left
 - Liver right
 - Spleen
 - Subcutaneous/cutaneous
 - Muscle
 - Bowel
- Bones
 - o Skull
 - Skull base/maxilla left
 - Skull base/maxilla right
 - Mandible left
 - Mandible right
 - Vertebra
 - Vertebra C1
 - Vertebra C2
 - Vertebra C3
 - Vertebra C4

- Aorto-caval
- Retrocrural left
- Retrocrural right
- Axillary right
- Cervical left
- Cervical right

Vertebra C5

Vertebra C6

Vertebra C7

Vertebra T1

- Vertebra T2
- Vertebra T3
- Vertebra T4
- Vertebra T5

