5.4 Statistical Analysis

5.4.1 Primary Efficacy Analysis

The analysis of the primary outcome will be performed on the EAS as the primary analysis and will be repeated on the PPS as a secondary analysis. Comparisons between the original treatment plan and the revised treatment plan will be categorised as no change, major change or other change. The definitions of the change categories are listed below.

- No change: the original treatment plan is the same as the revised treatment plan
- Major change: the original treatment plan is not the same as the revised treatment plan and the grouping for the original treatment plan is not the same as the grouping for the revised treatment plan

These will be further split and presented according to the following categories:

- Salvage or Non-curative systemic therapy to Watchful waiting
- Salvage therapy to Non-curative systemic therapy
- Non-curative systemic therapy to Salvage therapy
- Alternative Major change
- Other change: the original treatment plan is not the same as the revised treatment plan but the grouping for the original treatment plan is the same as the grouping for the revised treatment plan

These will be further split and presented according to the following categories:

- Modified RT field plan
- Modified androgen-deprivation regimen
- Alternative Other change

Groupings of treatment plans are detailed in the following table:

Date: 10OCT2018 Version: Amendment 1 Final

Version: Amendment 1 Fina ST/form/010/6

Original Treatment Plan	Grouping for Original Tx Plan	Revised Treatment	Grouping for Revised Tx Plan
Was androgen deprivation therapy planned	Androgen Deprivation Therapy	Androgen deprivation therapy	Androgen deprivation therapy
		Watch and wait	Watch and wait
		Chemotherapy	Chemotherapy
Salvage radiotherapy to the prostate bed		Salvage radiotherapy to the prostate bed	
Salvage radiotherapy to the prostate bed, with boost to areas guided by conventional imaging	Salvage Radiotherapy	Salvage radiotherapy to the prostate bed, with boost to areas guided by conventional imaging	Salvage Radiotherapy
		Salvage radiotherapy to the prostate bed with boost to areas guided by fluciclovine (18F) PET/CT	
Salvage radiotherapy to the prostate bed and whole pelvis		Salvage radiotherapy to the prostate bed and whole pelvis	

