5.4.2 Secondary Efficacy Analyses

5.4.2.1 Treatment response as assessed by change in PSA

An assessment of treatment response, which is based on the percentage change in PSA from baseline to the last value reported, is defined as:

- >=30% decrease in PSA will be considered to be a response to treatment
- <25% increase or <30% decrease will be classified as stable disease
- >=25% increase in PSA will be classified as disease progression

See section 2 General Principles for baseline definition.

The number, percentage and exact 95% CI of subjects having a treatment response, stable disease and disease progression, as assessed by change in PSA, will be presented overall and separately for subjects in the FAS who had salvage treatment, for subjects who had non-salvage treatment, for those with a change in management plan and for subjects with no change in management plan following the ¹⁸F-fluciclovine PET/CT scan. In addition, treatment response assessed by change in PSA will be summarised by disease location (local disease versus extra-prostatic disease) and treatment administered.

The percentage change in PSA from baseline to the last value reported will be summarised overall and by subjects who had a change in management plan versus those who did not have a change in management plan following the ¹⁸F-fluciclovine PET/CT scan, disease location and treatment administered.

Finally, a waterfall plot of the maximum percentage reduction in PSA during the 4-8 month window will be presented on the y-axis and each subject will be represented by a bar on the x-axis. The bars will be ordered in descending order of the magnitude of the percentage change in PSA value.

Treatment response and the factors used to assess the response will be listed in full.

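### The salvage response proportion cannot show improvement: the scan influences who is in its denominator, and the plan has no comparator

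*Protocol*

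**What the plan says.** Protocol section 4 states secondary objective 1: "To assess possible improvement in outcome of radical salvage treatment based on fluciclovine (¹⁸F) PET/CT being included in the assessment". Protocol 11.2 then defines the measure: "This will be assessed as the proportion of these patients who have a treatment response or treatment failure". Read with the line above it, this means the patients given radical salvage. SAP 5.2 names the variable as "The proportion of subjects who have a sustained response to radical salvage therapy", and SAP 5.4.2.1 tabulates PSA response overall and "separately for subjects in the FAS who had salvage treatment". It adds rows for non-salvage treatment, plan changed and plan unchanged, and summaries by disease location and by treatment administered.

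Addendum 2, Change 1, gives this same objective as its reason. Its new table is again confined to salvage-treated subjects, divided by whether the text of the agreed therapy says that it was guided by fluciclovine.

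On comparison, Protocol 7.4 says: "All participants will receive fluciclovine (¹⁸F) injection". Neither document gives a historical or null value for salvage response.

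On who receives salvage, entry requires that "The subject is being considered for radical salvage therapy" (Protocol 6.2). Protocol 3.5 notes that "the presence of disease outside the prostate bed precludes radical salvage therapy based on mainstream practice". SAP 5.4.1 lists "Salvage therapy to Non-curative systemic therapy" among the major changes. It also lists the reverse move, and its table of revised plans includes targeted salvage of scan-positive sites outside the pelvis or in bone.

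**The concern.** The test being evaluated helps to decide who enters the denominator of its own outcome measure. If the subjects it takes out of salvage would have done worse than those it leaves in, the response proportion among the treated rises although each patient's own outcome is unchanged. This is stage migration. The indirect support for that direction is in Protocol 3.3, where patients with a negative choline PET/CT had better outcomes than those with a positive one.

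What is at stake is the conclusion on secondary objective 1. Improvement is a comparative claim. The plan supplies one uncontrolled proportion on a group shaped by the scan, and nothing in the SAP tells the reader that the figure cannot carry that claim. The primary endpoint is not affected.

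**Working it through.** **Figure in the plan.** There is none for this endpoint. The only sample size calculation is for the primary endpoint: 1.96² × 0.20 × 0.80 / 0.06² = 170.7, so 171, and 171/0.95 = 180. It reproduces, but it says nothing about salvage response.

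**Inputs, all assumed because the documents give none.** f is the share of pre-scan salvage-intent patients moved off salvage. r_kept is the response to salvage in those who stay, set at 70%. r_removed is the response that those moved off would have had if salvaged.

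**Formula.** Response if all had been salvaged = (1 − f) × r_kept + f × r_removed. Response in those still treated = r_kept. The difference is f × (r_kept − r_removed).

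**Worked case.** With f = 20% and r_removed = 40%, all-salvaged = 0.80 × 0.70 + 0.20 × 0.40 = 64.0%. The treated-only figure is 70.0%, a shift of +6.0 points.

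**Range of the shift, in points:**

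| f | r_removed 20% | 40% | 50% | 70% | 80% |
|---|---|---|---|---|---|
| 10% | +5.0 | +3.0 | +2.0 | 0 | −1.0 |
| 20% | +10.0 | +6.0 | +4.0 | 0 | −2.0 |
| 40% | +20.0 | +12.0 | +8.0 | 0 | −4.0 |

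**Moves into salvage.** Let a further share m (of the same base) enter salvage with 40% response, with f = 20%. The treated-only figure becomes (0.56 + 0.40m)/(0.80 + m):
- m = 5%: 0.58/0.85 = 68.2%
- m = 10%: 0.60/0.90 = 66.7%
- m = 20%: 0.64/1.00 = 64.0%, so the shift has gone.

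**Does the overall row in SAP 5.4.2.1 repair this?** It adds PSA falls produced by the replacement treatment. With f = 20% and an assumed PSA response of 90%, 40% or 10% on that treatment, overall is 0.56 + 0.20 × 0.90 = 74%, 64% or 58%, against 64% had all been salvaged. It does not isolate salvage outcome.

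**Does the Addendum 2 split repair it?** No. Both groups were scanned and both are limited to subjects who received salvage, so the not-guided group is not an unscanned comparator.

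**What if everyone moved off salvage counts as a non-responder?** The worked case then gives 0.80 × 0.70 = 56%, against 64% had all been salvaged. That row is biased downward.

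**The case against.** A reader might infer that selection must push the figure up and so favour the product. The documents do not support that. SAP 5.4.1 foresees moves into salvage and targeted salvage of extra-prostatic sites, and Protocol 3.4 describes an emerging role for salvage of limited nodal disease. Each can keep or bring harder cases into the salvage row. The upward shift is plausible but conditional, as the table shows.

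It is also tempting to size the effect with the plan's own percentages. The 25.7% is an up-staging rate from a comparison with capromab SPECT/CT (Protocol 3.6). The 20% in Protocol 11.1 is any treatment change. Neither is the share leaving salvage, so the 20% used for f is only an assumption.

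Nor do the documents plan a comparison with the salvage series in Protocol section 3. Those with outcome figures are mostly imaging-selected, and their PSA outcomes are mostly complete responses, a different measure from the one used here.

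Part of the matter is already covered. All participants were salvage candidates at entry, so the overall row includes them. Counts of subjects moving off salvage are planned, Addendum 2, Change 2, tabulates extra-prostatic findings in those moved to non-curative systemic therapy, and the individual plans are listed. Recruitment has also ended and Addendum 2 follows database lock, so rewording the protocol would now change nothing.

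These points limit the claim about direction and the form of the remedy. They do not supply a comparator or a row by pre-scan plan. Being considered for salvage is not the same as having salvage as the recorded plan, since SAP 5.4.1 also allows androgen deprivation as the pre-scan plan.

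**Conclusion.** The point holds in a limited form. The salvage-treated response proportion cannot serve as evidence of improvement, for two reasons: the scan influences who is counted, and there is nothing to compare the figure with. The second would remain even without selection.

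The distortion equals f × (r_kept − r_removed) before any moves into salvage. Under the assumptions shown, with 20% moved off, it runs from −2.0 to +10.0 points. It is zero when those removed would have responded equally well, or when equal numbers of similar patients enter salvage. Because the documents give none of these rates, neither size nor sign can be fixed from them. The conclusion rests on the structure of the endpoint and not on the illustrative numbers. It concerns one secondary objective and is cheap to put right.

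**What to change.** 1. State in the SAP or a further addendum, and in the report, that the salvage-treated proportion and its guided/not-guided split are descriptive. They are not evidence of improvement, because the scan influences the denominator and there is no comparator.
2. Add one table for subjects whose pre-scan plan was radical salvage. Show how many stayed on salvage and how many moved off. Give PSA response with exact 95% CI for the whole group whatever treatment followed, and separately by treatment received. Show beside it the number moved into salvage, and the number in the FAS with no recorded pre-scan plan. PSA baselines (SAP section 2) and follow-up windows (Protocol 7.7) differ between salvage and non-salvage subjects, so the whole-group figure should be read with the rows by treatment.
3. If a row counting subjects moved off salvage as non-responders is also shown, label it a lower bound that is biased downward.

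No new data are needed. The intended plan is recorded at Visit 1 (Protocol 7.5), and treatment received and PSA are collected at follow-up (Protocol 7.7). Addendum 2 shows that tables can be added after lock. The price is one extra table, labelled post hoc if added after lock, and a weaker statement on secondary objective 1. The new table does not establish improvement either; it shows what the scan did to the group.

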11.3. Interim Analysis

A single interim analysis of the primary endpoint was performed in the first 85 evaluable patients. The number of treatment changes was greater than 45 (52.9%, with a 97.5% two-sided C.I. of 40.3%-62.3%, so the lower limit is over 40%), the trial recruitment was terminated early due to overwhelming effectiveness. If the number of treatment changes would have been 8 or fewer (9.4%, with a 97.5% two-sided C.I. of 3.6%-18.9%, so the upper limit in this population would have been below the 20% of the null hypothesis), the trial would have been terminated early due to futility.

12. DATA MANAGEMENT

12.1. Access to Data

Direct access will be granted to authorised representatives from the Sponsor or host institution for monitoring and/or audit of the study to ensure compliance with regulations.

12.2. Data Recording and Record Keeping

Database considerations

Data collection will be done using a web-based eCRF and Data management will be managed by a contracted Clinical Research Organisation. The Chief Investigator will act as Data Custodian for the trial.

Case report forms

Data collected on each subject will be recorded by the research team as accurately and completely as possible. The Investigator will be responsible for the timeliness, completeness, legibility and accuracy of the CRFs. Each patient enrolled into the study must have the correct CRFs completed and signed by the Principal Investigator (or designee). This also applies to those patients who have been withdrawn early. Please ensure that all data submitted on CRFs are verifiable in the source documentation or the discrepancies explained.

Records retention and archiving

During the clinical trial and after trial closure the Investigator must maintain adequate and accurate records to enable the conduct of a clinical trial and the quality of the research data to be evaluated and verified. These essential documents (as detailed in Section 8 of the ICH GCP Guidelines) must be stored in such a way that ensures that they are readily available, upon request for the minimum period required by national legislation or for longer if needed. The medical files of trial subjects shall be retained in accordance with national legislation and in accordance with the host institution policy. Data entered onto the eCRFs will be returned to the sites in CD format and must be checked for accuracy and then held with the study files. Data will be retained on site for a minimum of 5 years. Retention and storage of scanning records for clinical scans must also follow these guidelines.

Imaging data for central review

Copies of the fluciclovine (¹⁸F) PET/CT scan and PET/CT report will be made for central review and analysis. Retention and archiving of this data will be performed according to the guidelines stipulated in this section.

